6.3. Safety Observations and Measurements

Hepatic complication events occurring as described in the patient's file from the time of enrollment in the previous pivotal study and the time of this proposed investigation will be recorded.

6.4. Concomitant Medications and Therapies

All concomitant medications administered as described in the patient's file from the time of enrollment in the previous pivotal study and the time of this proposed investigation will be recorded. all medication prescribed from the time of enrollment to the time of this proposed investigation as described within the patient's file will all be recorded.

6.5. Subject Completion and Withdrawal

Not applicable.

7. INVESTIGATIONAL NEW DRUG USED IN THE STUDY

Not applicable.

7.1. Treatment of Overdose

Not applicable

| | |
|--|--|
| Exalenz Bioscience Ltd. | Last update on: April 01, 2015 |
| Protocol: The predictive value of the BreathID, ¹³ C-Methacetin breath test for Hepatic Decompensation; a retrospective analysis | Version Level: 1b |
| Document No.: CSD00074 | Page 15 of 23 |

8. STATISTICAL CONSIDERATIONS

8.1. Study Design and Objectives

This is a retrospective, multi-center, non-randomized, open label study of the ¹³C-Methacetin BreathID Test (MBT) that will include all patients previously enrolled into the BreathID pivotal study who have performed a valid MBT.

The main objective of the study is to evaluate the ability of the MBT to predict time to hepatic decompensation events.

The secondary objective of the study is show that MBT predictive ability is better than that of liver biopsy/MELD in predicting time to these events.

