It is anticipated that 3-5% of patients with stable cirrhosis will develop hepatic decompensation and achieve an end-point within a year. An additional 1-2% would be expected to die from these complications per year. This study is conducted 6 years post initial enrollment, accordingly the expected amount of complications are expected to be 6 times higher. Furthermore some of the patients that were not considered as cirrhotic at the time of enrollment may progress to cirrhosis and deteriorate.

| | |
|--|--|
| Exalenz Bioscience Ltd. | Last update on: April 01, 2015 |
| Protocol: The predictive value of the BreathID, ¹³ C-Methacetin breath test for Hepatic Decompensation; a retrospective analysis | Version Level: 1b |
| Document No.: CSD00074 | Page 6 of 23 |

All patients with valid breath test results from the HIS-EX-408 and/or PLT-BID-1108 trials will be candidates for this follow up trial.

Analyses:

All statistical analyses and data presentations, including tabulations and listings, will be performed using the SAS version 9.3 (or higher) software. Statistical tests will be two-sided and the level of significance is 0.05. Nominal p-values will be presented.

The ability of MBT to predict morbidity and mortality and other complications will be evaluated using survival analysis methods, mainly Kaplan-Meier curves and Cox regression analyses.

| | |
|--|--|
| Exalenz Bioscience Ltd. | Last update on: April 01, 2015 |
| Protocol: The predictive value of the BreathID, ¹³ C-Methacetin breath test for Hepatic Decompensation; a retrospective analysis | Version Level: 1b |
| Document No.: CSD00074 | Page 7 of 23 |

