1.10. Summary of Overall Risk and Benefits

Since this proposed study is retrospective no adverse events and/or risk associated with the MBT are expected.

The MBT BreathID system consists of the device and ¹³C-Methacetin. The same device but with a different substrate (¹³C-Urea) for the diagnosis of H. Pylori was cleared as a 510(K). The software of the cleared device was upgraded in order to allow the BreathID system to be used in the assessment of liver disease severity. Therefore, the BreathID device does not pose any increased risk to patients participating in this study.

| | |
|--|--|
| Exalenz Bioscience Ltd. | Last update on: April 01, 2015 |
| Protocol: The predictive value of the BreathID, ¹³ C-Methacetin breath test for Hepatic Decompensation; a retrospective analysis | Version Level: 1b |
| Document No.: CSD00074 | Page 11 of 23 |

The ¹³C-methacetin substrate has been used for various breath tests in numerous patients including special populations such as neonatals and pregnant women. To the best of our knowledge no adverse events had ever been reported using ¹³C-Methacetin.

Furthermore, Methacetin is a well known drug that has been available and described in literature for over 30 years and is currently used in medications (such as acetaminophen) for human therapeutic use. No risks have been reported in literature using much higher doses of Methacetin than currently used in the MBT.

During the test procedure, patient contact with the device is through a nasal cannula for collection and analysis of the breath samples. Nasal breathing cannulae are a well-known and proven medical tool having minimum side effects. No discomfort has been reported during prior feasibility studies conducted by Exalenz involving over 400 patients performed with the nasal cannula.

The data analyzed in this study will be used to validate the hypothesis claiming a single ¹³C-Methacetin breath test in chronic liver patients may correlate with liver related morbidity and mortality. This claim had been already been demonstrated in previous studies done by the company, showing a hazard ratio of up to 12 between a single MBT and complications and mortality in chronic patients within one year of the breath test. If such a claim is to be validated, it is expected to influence the clinical practice for such patients preventing the onset of complications and death.

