8.6. Statistical Analyses

All statistical analyses and data presentations, including tabulations and listings, will be performed using the SAS version 9.3 (or higher) software. Statistical tests will be two-sided and the level of significance is 0.05. Nominal p-values will be presented.

Baseline demographics and medical characteristics will be presented in tabular format. The statistical evaluation of baseline characteristics will include all available data.

For continuous variables, the following descriptive statistics will be given: N, Mean, Standard Deviation, Minimum, Median and Maximum values; for discrete variables, the Frequency and Percentage of patients or events will be provided.

For comparison of means (continuous variables), the two-sample t-test or the Wilcoxon rank sum test will be used as appropriate. For comparison of proportions (categorical variables), the Chi-squared test or Fisher's exact test will be used as appropriate.

Kaplan-Meier curves of the time event data will be presented. For comparison of time to event data, the log rank test will be used. Cox regression will be used to estimate hazard ratios, their level of significance and 95% confidence limits.

Risk stratification may be performed by categorizing the MBT into risk groups, for these groups Kaplan-Meier Curves of the time to clinical outcome will be presented for the MBT categories as well as the liver biopsy results to compare predictive value.

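### The main objective is prediction, but the plan has no measure of discrimination and makes absolute risk by breath test result optional

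*Combined protocol and SAP*

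**What the plan says.** Section 8.1 gives the main objective: "The main objective of the study is to evaluate the ability of the MBT to predict time to hepatic decompensation events". Its secondary objective is to "show that MBT predictive ability is better than that of liver biopsy/MELD in predicting time to these events".

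The synopsis, under Analyses, says that the ability to predict is to be "evaluated using survival analysis methods, mainly Kaplan-Meier curves and Cox regression analyses". Section 8.6 fills this in:
- On comparing groups, it says: "For comparison of time to event data, the log rank test will be used".
- On the size of effect, it says: "Cox regression will be used to estimate hazard ratios, their level of significance and 95% confidence limits".
- On significance, it says: "Statistical tests will be two-sided and the level of significance is 0.05. Nominal p-values will be presented".

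Section 8.6 also lists t or Wilcoxon tests for means and chi-squared or Fisher tests for proportions, without tying them to the MBT. It allows, but does not require, the MBT to be cut into risk groups and shown as Kaplan-Meier curves beside the biopsy results. It gives no cut-points and no time horizon. It does not say whether the MBT enters the Cox model as a continuous or a grouped variable.

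Section 1.10 describes the purpose: "The data analyzed in this study will be used to validate the hypothesis claiming a single" breath test may be correlated with liver-related illness and death. It cites an earlier hazard ratio of up to 12 within one year and expects a validated claim to influence practice.

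**The concern.** A hazard ratio different from 1 shows that the MBT is associated with the rate of events. It does not show how well the MBT ranks patients by time to decompensation, or what risk a given result carries. The objective asks about prediction, and the planned outputs answer mainly about association.

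No concordance index, time-dependent AUC, sensitivity, specificity, predictive value, calibration measure or minimum performance level appears in the protocol or its statistical section. No success criterion is written either. A nominally significant hazard ratio could therefore be reported as predictive ability when the test barely sorts patients. This matters because section 1.10 expects the result to affect the care of chronic liver patients, and a clinician acting on a single test needs its discrimination and absolute risks.

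**Working it through.** **The plan's own figure.** Section 8.5 gives the maximum sample size as 414 + 165 = 579, which reproduces. It states no target effect, power or number of events, so there is nothing else to reproduce.

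**Events.** The synopsis expects 3-5% of patients with stable cirrhosis to reach an endpoint each year, and six times that over 6 years:
- 6 × 3% = 18%, and 579 × 0.18 ≈ 104 events.
- 6 × 5% = 30%, and 579 × 0.30 ≈ 174 events.

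The cohort is mixed chronic liver disease and 579 is a maximum, so these counts are assumptions. Compounding gives 1 − 0.97⁶ = 16.7% and 1 − 0.95⁶ = 26.5%, which does not change the conclusion. Lower counts of 30, 60 and 100 are assumed as well, to show the range.

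**Smallest significant effect.** For a marker scaled to 1 SD, two-sided p = 0.05 is reached at ln(HR) = 1.96/√E, where E is the number of events. At 104 events, 1.96/√104 = 0.192 and HR = 1.21.

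**Concordance at that effect.** For a normally distributed marker under proportional hazards, C is the mean of 1/(1 + exp(−b|D|)), where b = ln(HR) and D is the difference between two patients (variance 2). This is close to Φ(b/√2). Chance is C = 0.50.

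| Events | Source | Just-significant HR per SD | C |
|---|---|---|---|
| 30 | assumed | 1.43 | about 0.60 |
| 60 | assumed | 1.29 | about 0.57 |
| 100 | assumed | 1.22 | about 0.55 |
| 104 | 18% of 579 | 1.21 | about 0.55 |
| 174 | 30% of 579 | 1.16 | about 0.54 |

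**If the MBT is split at its median.** ln(HR) = 1.96/√(E/4), and C = 0.5 × HR/(1 + HR) + 0.25, with ties counted as one half. At 104 events HR = 1.47 and C is about 0.55. At 174 events HR = 1.35 and C is about 0.54.

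**Beyond the boundary case.** The effect with 80% power is ln(HR) = (1.96 + 0.84)/√E:
- At 104 events: HR 1.32, C about 0.58.
- At 174 events: HR 1.24, C about 0.56.

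In 400 simulated datasets for each of these two settings, 78% and 79% were significant, with mean C of 0.58 and 0.56. Among the significant datasets only, mean C was 0.59 and 0.57. A true effect with weak discrimination would thus usually reach p < 0.05.

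**Can the data support a discrimination estimate?** The Hanley-McNeil standard error for an AUC of 0.70 with 60 events and 519 non-events is 0.039. The 95% half-width is 1.96 × 0.039 ≈ 0.08. This ignores censoring, so it is only a guide, but the interval would be usable.

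**The case against.** Five points can be made for the plan.

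1. A reader might infer that p < 0.05 on a hazard ratio is the plan's rule for declaring the MBT validated. The documents do not say so. The 0.05 level is general to all tests, p-values are nominal, and no primary test or success criterion is named. What stands is that nothing in the plan stops such a result from being reported as predictive ability.

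2. Section 1.10 frames the hypothesis as correlation, which Cox regression can test. That is fair to section 1.10, but the main objective in 8.1 is about prediction, and 1.10 itself expects the claim to influence practice.

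3. A reader might infer that the plan offers no absolute risk at all. That is too strong. Kaplan-Meier curves by MBT group would show event risk at every time point. They are optional, however, and have neither cut-points nor horizons.

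4. The synopsis says the methods are mainly Kaplan-Meier and Cox, and 8.6 lists other tests, so the list is not closed. None of the named methods is assigned to estimating discrimination for a censored outcome.

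5. The just-significant effect is a boundary case. Section 1.10 cites an earlier hazard ratio of up to 12, without giving its scale. If it came from a median split, C would be 0.5 × 12/13 + 0.25 ≈ 0.71. A strong marker would look strong under either analysis. The planned confidence limits would also hint at a weak one, since at p = 0.05 one limit lies at 1. This stands, and it limits the point to what the plan commits to reporting.

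**Conclusion.** The concern holds as a gap between objective and analysis. The plan sets out to evaluate predictive ability but commits to no measure of discrimination, and it leaves absolute risk by MBT group optional and unspecified.

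On the synopsis rates, a hazard ratio of 1.21 to 1.16 per SD would be nominally significant with C of only about 0.55 to 0.54. With as few as 30 events, C at the boundary is still only about 0.60. These figures rest on 579 patients, a normally distributed marker, proportional hazards, and a stable-cirrhosis event rate applied to a mixed cohort.

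A reader might go further and infer that the MBT discriminates poorly. Nothing in the documents shows that. The figures show only that significance alone cannot tell a weak test from a useful one. The gap should be closed before the analysis, and it does not invalidate the study.

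**What to change.** In section 8.6:

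- Report, alongside the Cox hazard ratio, the MBT's concordance index (or time-dependent AUC) for time to first event, with a 95% confidence interval.
- Report Kaplan-Meier event risk with 95% confidence intervals at fixed horizons, for example 1, 3 and 5 years, by MBT groups whose cut-points are fixed before outcomes are examined.
- Give sensitivity, specificity and negative predictive value only at such a pre-fixed cut-point.
- Base any statement of predictive ability on these measures, and describe a significant hazard ratio alone as an association.

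The cost is some wording in the statistical section and a few more outputs from data already held. The drawback for the sponsor is a headline that may look less favourable than a hazard ratio.

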8.2. Primary Endpoint

The MBT results and the time to hepatic decompensation events:

Hepatic decompensation event is defined as the occurrence of at least one of the following events in the time frame between the last ¹³C Methacetin Breath Test (MBT) to the time of data collection:

1. Death (liver related)
2. Transplantation (cadaveric and living donors)
3. Ascites
4. HE (Hepatic Encephalopathy)
5. Newly diagnosed varices or variceal bleeding
6. SBP (spontaneous bacterial peritonitis)/Sepsis
7. HRS (Hepatorenal syndrome)
8. HCC (Hepatocellular carcinoma)
9. Increase in CTP (Child Turcotte Pugh) Score by 3 points
10. Increase in MELD score by 5 points

.

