| Document No.: CSD00074 | Page 3 of 23 |

| | | |
|---------|--|----|
| 8. | STATISTICAL CONSIDERATIONS..... | 15 |
| 8.1. | STUDY DESIGN AND OBJECTIVES..... | 15 |
| 8.2. | PRIMARY ENDPOINT | 15 |
| 8.3. | SECONDARY ENDPOINT | 15 |
| 8.4. | SAFETY ENDPOINTS | 15 |
| 8.5. | SAMPLE SIZE..... | 15 |
| 8.6. | STATISTICAL ANALYSES..... | 16 |
| 9. | ADVERSE EVENTS..... | 16 |
| 10. | STUDY ADMINISTRATION..... | 16 |
| 10.1. | REGULATORY AND ETHICAL CONSIDERATIONS | 16 |
| 10.1.1. | Informed Consent | 16 |
| 10.1.2. | Institutional Review Board | 16 |
| 10.1.3. | End of the study | 17 |
| 10.2. | INVESTIGATOR RESPONSIBILITIES | 17 |
| 10.3. | DATA MANAGEMENT | 17 |
| 10.4. | STUDY MONITORING | 17 |
| 10.5. | SUBJECT CONFIDENTIALITY | 17 |
| 10.6. | QUALITY ASSURANCE..... | 18 |
| 10.7. | RETENTION OF ESSENTIAL STUDY DOCUMENTS | 18 |
| 10.8. | AGREEMENTS..... | 18 |
| 11. | PUBLICATION | 18 |
| 12. | REFERENCES..... | 18 |

| | |
|--|--|
| Exalenz Bioscience Ltd. | Last update on: April 01, 2015 |
| Protocol: The predictive value of the BreathID, ¹³ C-Methacetin breath test for Hepatic Decompensation; a retrospective analysis | Version Level: 1b |
| Document No.: CSD00074 | Page 4 of 23 |

SYNOPSIS

Investigational Product:

0.05% ¹³C-Methacetin solution and the BreathID® Device

Phase of Development:

Retrospective clinical investigation

Background:

This study is a follow up study to be conducted in selected sites, that participated in Exalenz' Pivotal HIS-EX-408 and/or PLT-BID-1108 study using the MBT in chronic liver patients. The aim of the study was to compare the breath test to the liver biopsy to assess the capability to detect cirrhosis.

Study Rationale:

Previous studies have shown that the MBT can be used to predict liver decompensation. In the present study Exalenz wishes to evaluate the prognostic value of MBT and Biopsy in a long term retrospective surveillance of the described study population.

Objectives:

To evaluate the ability of the MBT to predict hepatic decompensation events, in patients with chronic liver disease.

Primary outcome measures: MBT results and Hepatic decompensation measured with the time to each event, defined as the occurrence of at least one of the following events in the time frame between the last ¹³C-Methacetin Breath Test (MBT) to the time of data collection:

1. Death (liver related)
2. Transplantation (cadaveric and living donors)
3. Ascites
4. HE (Hepatic Encephalopathy)

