3. ENDPOINTS

3.1. Primary Efficacy Endpoints

The MBT results and the time to hepatic decompensation events:

Hepatic decompensation is defined as the occurrence of at least one of the following events in the time frame between the last ¹³C-Methacetin Breath Test (MBT) to the time of data collection:

1. Death (liver related)
2. Transplantation (cadaveric and living donors)
3. Ascites
4. HE (Hepatic Encephalopathy)
5. Newly diagnosed varices or variceal bleeding
6. SBP (spontaneous bacterial peritonitis)/Sepsis
7. HRS (Hepatorenal syndrome)
8. HCC (hepatocellular carcinoma)
9. Increase in CTP (Child Turcotte Pugh) Score by 3 points
10. Increase in MELD score by 5 points

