5.1. Entry Criteria

5.1.1. Inclusion Criteria (screening visit)

To be eligible for inclusion into this study, the subjects must fulfill all of the following criteria:

- Previously enrolled into a BreathID Methacetin study according to study protocol.
- Has a valid Methacetin breath test result.
- Patient file is available for review.

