10.1.2. Institutional Review Board

Before initiation of the study at a given center, written approval of the protocol, and waiver for the Informed Consent Form must be approved from the appropriate IRB. If any amendments to any of these documents occur during the study, written approval must be obtained prior to their implementation.

| | |
|--|--|
| Exalenz Bioscience Ltd. | Last update on: April 01, 2015 |
| Protocol: The predictive value of the BreathID, ¹³ C-Methacetin breath test for Hepatic Decompensation; a retrospective analysis | Version Level: 1b |
| Document No.: CSD00074 | Page 17 of 23 |

10.1.3. *End of the study*

For administrative reporting purposes the end of the study will be defined as the date of the final clinical database lock. This provides for a single and conservative definition across all study sites.

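### Does the lack of a stated censoring rule for patients whose files end before data collection call for a change to the plan?

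*Combined protocol and SAP*

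**What the plan says.** Sections 3.1 and 8.2 and the Synopsis define the primary endpoint over one window: from the last "Methacetin Breath Test (MBT) to the time of data collection". Time zero is therefore fixed. The end of the window is named but carries no calendar date.

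Outcomes come from existing records. Section 5.1.1 requires that "Patient file is available for review" but sets no minimum follow-up. Section 6.3 says that hepatic complications "from the time of enrollment in the previous pivotal study and the time of this proposed investigation will be recorded", and section 6.4 uses the same span for medication. Neither these sections nor the list in 6.2.1 names a date of last contact. Section 6.5, "Subject Completion and Withdrawal", is marked not applicable. Section 10.1.3 adds: "For administrative reporting purposes the end of the study will be defined as the date of the final clinical database lock".

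Section 8.6 specifies Kaplan-Meier curves, the log rank test and Cox regression, with no text on censoring. Only liver-related death is an endpoint component, and nothing says how follow-up ends after a death from another cause.

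The Synopsis (Statistical Analysis, Introduction) gives 3-5% a year for decompensation in stable cirrhosis and expects six times as many complications because the study takes place six years after initial enrollment. Breath tests ran from August 2008 to September 2012.

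**The concern.** In a file-review study, absence of a recorded event does not show that a patient was observed and event-free. Someone who left the clinic in 2011 and someone seen last month can look alike. The only end of follow-up that the plan names is data collection, so a literal reading could keep both at risk until then.

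That would add person-time in which no event could have been seen. Cumulative risk would come out too low, and the hazard ratio for the breath test, the main result, would be biased if loss differed by breath-test level. This bias does not shrink as the cohort grows. Three side issues looked related: no common calendar cut-off, a start date in 6.3 that differs from 8.2, and a six-times expectation that cannot fit patients tested as late as 2012.

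**Working it through.** **Inputs from the documents.** Maximum cohort 414 + 165 = 579 (section 8.5, reproduced). Annual risk 3-5% in stable cirrhosis (Synopsis). Test dates August 2008 to September 2012 (Synopsis).

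**Assumptions.** Data collection on 1 April 2015, which is the protocol's last-update date and only a proxy. Test dates uniform, so potential follow-up C runs from 2.50 to 6.66 years (mean 4.58). True hazard ratio 3, low versus high breath test. Average hazard 0.04 a year. Share p with a low test 30% or 50%. All loss rates are assumed; the documents give none.

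**1. Hazard ratio if patients are carried to data collection.** With group hazards λ0 and 3λ0, λ0 = 0.04/(1 − p + 3p) = 0.025 (p = 0.3) or 0.020 (p = 0.5). A yearly loss probability q gives loss hazard μ = −ln(1 − q). In each group, with λ its event hazard:

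- density of events seen: λ·exp(−(λ+μ)t)·P(C ≥ t)
- proportion counted at risk if carried forward: P(C ≥ t)·[1 − λ/(λ+μ)·(1 − exp(−(λ+μ)t))]

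Weighting the groups by 1 − p and p and solving the Cox score equation gives:

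| Yearly loss, high test / low test | HR, p = 0.3 | HR, p = 0.5 |
|---|---|---|
| 3% / 3% | 2.98 | 2.99 |
| 5% / 5% | 2.97 | 2.98 |
| 10% / 10% | 2.95 | 2.96 |
| 3% / 5% | 2.83 | 2.83 |
| 5% / 3% | 3.13 | 3.14 |
| 5% / 10% | 2.61 | 2.62 |
| 10% / 5% | 3.35 | 3.36 |

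**2. Size against sampling error.** Complete follow-up of 579 patients yields about 94 events. SE of log HR ≈ 1/√(94·p·(1 − p)) = 1/√19.74 = 0.225 (p = 0.3) or 1/√23.5 = 0.206 (p = 0.5). The 5% v 10% shifts are ln(2.61/3) = −0.14 and ln(3.36/3) = +0.11, about half to two thirds of one SE. With the 77 to 81 events seen in those scenarios the same formula gives 0.22 to 0.25, so the relative shift is smaller still.

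**3. Absolute risk.** True five-year risk for p = 0.3 is 1 − [0.7·exp(−0.125) + 0.3·exp(−0.375)] = 17.6%; for p = 0.5 it is 17.7%. Carried forward, the pooled Kaplan-Meier figure is 16.4-16.5%, 15.6-15.7% or 13.8-13.9% with equal yearly loss of 3%, 5% or 10%.

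**4. A different loss model.** Suppose a fixed share of files ends at a uniform time before collection, with a true HR of 2. Carrying forward gives 2.0 when 20% end early in both groups, 1.79 when 30% of high-risk and 10% of low-risk files do, and 2.24 with those shares reversed. Censoring at the last record returns 2.0 each time.

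**5. Side issues.**

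- *Site cut-offs.* Different collection dates are administrative censoring. With site ends staggered by up to 1.5 years and no loss, a simulation returned HR 2.98-2.99 for a true 3.
- *Start date.* Section 6.3 sets what is recorded, and 8.2 sets what is analysed. Recording a wider span does not conflict with a time zero at the last test.
- *Six times.* 6 × 3% = 18% and 6 × 5% = 30%. As first-event risk over six full years, 1 − 0.97^6 = 16.7% and 1 − 0.95^6 = 26.5%. Averaged over the assumed 2.50-6.66 years, 13.0% and 20.8%. The sentence is loose, but section 8.5 takes the whole available cohort and states no power or event target, so no figure depends on it.

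**The case for a change.** The strongest reply is that survival methods require a censoring time but do not supply one. The plan's only candidate is data collection, and the date needed for a better rule is not among the items listed for collection. If the paper CRF lacks it, files may have to be reopened. Section 8.6 also uses Kaplan-Meier curves to compare breath-test categories with biopsy, and those curves are too low under carry-forward even when loss is equal.

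Part of this stands. One sentence on censoring would make the plan clearer, and absolute risks are the results most exposed. Non-liver death is also left to the analyst. Ending follow-up there gives a cause-specific hazard ratio, and the Kaplan-Meier risk then reads high if competing deaths are common. Censoring at last contact is not perfect either: with loss that also tracked unmeasured severity, it gave 2.83 to 3.00 against a true 2.89 to 2.93 in simulation.

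The rest does not carry. The window in 8.2 says which events count; it does not say that an unobserved patient is event-free. The CRF is not among the documents, so a missing date field is unproven, and the file itself must be available for every included patient. An analyst running these methods on chart data would ordinarily stop follow-up at the last record.

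**Conclusion.** No change follows. The omission is real, but it is missing detail that the choice of methods leads an analyst to fill sensibly, and the plan contains no instruction that would produce the bias. Under modest assumed differences in loss, even the wrong choice moves the hazard ratio by less than one standard error (0.11-0.14 against 0.21-0.23), and equal loss barely moves it. The understatement of five-year risk, about 1 to 4 percentage points for equal yearly loss of 3-10%, arises only under carry-forward.

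These sizes rest on assumed loss rates, a true hazard ratio of 3, a 4% yearly rate taken from the stable-cirrhosis range although the cohort is broader, the full 579 patients, uniform test dates and a proxy collection date. Much more unequal loss would matter more, but nothing in the documents points to it. The cut-off, start-date and six-times points are ordinary administrative censoring, a harmless wider recording window, and loose wording with no dependent figure.
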